In patients receiving BI 655066 either i.v. (n=18) or s.c. (n=13), 87% achieved at least 75% reduction in Psoriasis Severity and Area Index (PASI 75) by Week 12, compared to none in the placebo group. Twenty four weeks after a single administration of BI 655066, 71% of patients maintained at least a PASI 75; nearly half (48%) had 90% reduction in PASI (PASI 90) and 29% had complete resolution of lesions (PASI 100). A protocol amendment allowed an optional extension of follow-up beyond Week 24 for patients in the s.c. dose cohort; six of thirteen originally enrolled patients maintained a PASI 100 improvement for 41–66 weeks after treatment.

After a single i.v. administration, BI 655066 geometric mean $AUC_{0-\infty}$ ranged from 2.93–1650 day*µg/mL and C_{max} from 0.311–110 µg/mL, with exposure increasing in a dose-proportional manner. Group mean clearance and terminal phase volume of distribution were 0.33 L/day and 10.8 L, respectively. PK parameter variability, expressed as gCV (%) was <50%. After a single s.c. administration of BI 655066, maximal exposures were reached between 5–13 days and subcutaneous bioavailability was 73% (expressed as the ratio of geometric mean dose normalised $AUC_{0-\infty}$ after s.c. and i.v. administration).

For a more detailed description of the drug profile refer to the current Investigator's Brochure (IB) ([c01569420-06](#)) which is included in the Investigator Site File (ISF).

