6.2.3 Follow up Period and Trial Completion

For all randomized patients termination of trial medication and trial completion must be recorded on the corresponding eCRF.

The follow-up period within this trial is 16 weeks after receiving the last dose of study medication. Refer to the flow charts for the list of procedures required.

Early treatment and trial termination

If study medication is discontinued prior to the planned Flow Chart EOT visit, every effort should be made to have the patient continue in the trial and complete all of the remaining Treatment Period Visits, as well as Follow-Up 1 and Follow-Up 2 Visits. Trial termination should be completed at Follow-Up 2 Visit.

If a patient cannot or will not continue in the trial, the patient should complete EOT visit procedures instead of the planned treatment period visit and return to the clinic for Follow-Up 2/End of Observation (FU2/EOO) Visit 16 weeks after last dose of study medication.

Patients who discontinue treatment early should be registered as withdrawn/discontinued in IRT and will not have the option to participate in the OLE trial.

Successful trial completion

Patients who complete treatment according to the applicable planned Flow Chart visit schedule will return to the clinic for Follow-up Visit 1, (6 weeks after last dose of study medication) and for the EOO visit (16 weeks after last dose of study medication). Trial completion is defined as patients completing the EOO visit within the specified window per the flow charts, and who have not discontinued drug prematurely. These patients should be registered as completed in IRT at the EOO visit. These patients will have the option to participate in the open label extension (OLE) trial once EOO procedures are completed.

Refer to ISF for OLE trial entry details.

Vital Status

For randomized patients leaving the study early (before the planned EOO in their current applicable flow chart), vital status should be collected every 12 months after discontinuation up to the planned EOO.

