7.3.4 Safety analyses

Adverse events will be coded using the Medical Dictionary for Drug Regulatory Activities (MedDRA) coding dictionary. Standard AbbVie summary tables and listings will be produced. All adverse events with an onset between start of treatment and end of the residual effect period (REP), a period of 15 weeks days after the last dose of trial medication, will be assigned to the treatment period for evaluation.

All treated patients will be included in the safety analysis. In general, safety analyses will be descriptive in nature and will be based on AbbVie standards. No hypothesis testing is planned.

Statistical analysis and reporting of adverse events will concentrate on treatment-emergent adverse events. To this end, all adverse events occurring between start of treatment and end of the residual effect period will be considered 'treatment-emergent'. Adverse events that start before first drug intake and deteriorate under treatment will also be considered as 'treatment-emergent'.

Frequency, severity, and causal relationship of adverse events will be tabulated by system organ class and preferred term after coding according to the current version of the Medical Dictionary for Drug Regulatory Activities (MedDRA).

Laboratory data will be analysed both quantitatively as well as qualitatively. The latter will be done via comparison of laboratory data to their reference ranges. Values outside the reference range as well as values defined as clinically relevant will be highlighted in the listings.

Treatment groups will be compared descriptively with regard to distribution parameters as well as with regard to frequency and percentage of patients with abnormal values or clinically relevant abnormal values.

Vital signs, physical examinations, or other safety-relevant data observed at screening, baseline, during the course of the trial and at the end-of-trial evaluation will be assessed with regard to possible changes compared to findings before start of treatment.

More information on the analysis of safety will be given in the TSAP.

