b. The minimum of upper bound, the first dose date of retreatment with risankizumab for relapsed subjects (except the additional analysis as in footnote a), and within 105 days of last dose of study drug for safety analyses. If time is collected in vital signs, restrict to records prior to the first dose of retreatment.

Note: For additional PASI and sPGA analysis on ITT_B_R subjects re-randomized to risankizumab to evaluate continuous treatment, evaluations after retreatment with open label risankizumab will also be included along with blinded assessments.

Table 9. Visit Windows for Analysis of Safety Laboratory Tests and ECG in Part B (Safety_B_R/Safety_B_NR Populations)

Window Label	Target Day	Interval
Entry of B	1	≤ 1
Week 40	85	[2, 127]
Week 52	169	[128, 211]
Week 64	253	[212, 295]
Week 76	337	[296, 379]
Week 88	421	[380, 477]
Week 104	533	[478, 589 ^a]

Rx Day calculated relative to the first dose date of study drug in Part B. For re-randomized subjects not dosed in Part B, Rx Day calculated relative to the IRT date of Re-randomization evaluation.

a. The minimum of upper bound and first dose date of retreatment with risankizumab for relapsed subjects (and within 105 days of last dose of study drug for safety analyses).

Table 10. Visit Windows for Analysis of Other Efficacy Endpoints Only Collected at Week 52, 76, and 104 in Part B (ITT_B_R/ITT_B_NR/PP_B_R Populations)

Window Label	Target Day	Interval
Entry of B	1	≤ 1
Week 52	169	[2, 253]
Week 76	337	[254, 435]
Week 104	533	[436, 631 ^a]

Rx Day calculated relative to the first dose date of study drug in Part B. For re-randomized subjects not dosed in Part B, Rx Day calculated relative to the IRT date of Re-randomization evaluation.

a. The minimum of upper bound and first dose date of retreatment with risankizumab for relapsed subjects.

Table 11. Visit Windows for Analysis of PASI and sPGA Across Part A2 and B (ITT_ARM2 Population)

Window Label	Target Day	Interval
Entry of A2	1	≤ 1
Week 20	29	[2, 43]
Week 24	57	[44, 71]
Week 28	85	[72, 99]
Week 32	113	[100, 127]
Week 36	141	[128, 155]
Week 40	169	[156, 183]
Week 44	197	[184, 211]
Week 48	225	[212, 239]
Week 52	253	[240, 274]
Week 58	295	[275, 316]
Week 64	337	[317, 358]
Week 70	379	[359, 400]
Week 76	421	[401, 442]
Week 82	463	[443, 484]
Week 88	505	[485, 526]
Week 94	547	[527, 582]
Week 104	617	[583, 652]

Rx Day calculated relative to first dose date of risankizumab.

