Table 12. Visit Windows for Analysis of Other Efficacy Endpoints Collected at Week 28, 52, 76, and 104 in Part A2 and B (ITT_ARM2 Population)

Window Label	Target Day	Interval
Entry of A2	1	≤ 1
Week 28	85	[2, 169]
Week 52	253	[170, 337]
Week 76	421	[338, 519]
Week 104	617	[520, 715]

Rx Day calculated relative to first dose date of risankizumab.

Table 13. Visit Windows for Analysis of PASI and sPGA During Retreatment with Risankizumab (ITT_B_PBO_RT/ITT_B_RZB_RT Populations)

Window Label	Target Day	Interval
Entry of RTS	1	≤ 1
Week 8R	57	[2, 85]
Week 16R	113	≥ 86

Rx Day calculated relative to first dose date of retreatment with risankizumab.

Table 14. Visit Windows for Analysis of Other Efficacy Variables Only Collected at EOT and EOO Visits During Retreatment with Risankizumab (ITT_B_PBO_RT/ITT_B_RZB_RT Populations)

Window Label	Target Day	Interval
Entry of RTS	1	≤ 1
Week 16R	113	≥ 2

Rx Day calculated relative to first dose date of retreatment with risankizumab.

Table 15. Visit Windows for Analysis of Vital Signs and Local Tolerability in the ALL_RZB Population

Window Label	Target Day	Interval
Baseline	1	$\leq 1^a$
Week 4	29	[2, 43]
Week 8	57	[44, 71]
Week 12	85	[72, 99]
Week 16	113	[100, 155]
Week 28	197	[156, 239]
Week 40	281	[240, 323]
Week 52	365	[324, 407]
Week 64	449	[408, 491]
Week 76	533	[492, 575]
Week 88	617	[576, 673]
Week 104	729	[674, 785 ^b]

Rx Day calculated relative to first dose date of risankizumab.

- a. Local tolerability not measured at Baseline and at Week 104. If time is collected in vital signs, restrict to records prior to the first dose of risankizumab.
- b. The minimum of upper bound and within 105 days of last dose of risankizumab.

Table 16. Visit Windows for Analysis of Safety Laboratory Tests and ECG in the ALL_RZB Population

Window Label	Target Day	Interval
Baseline	1	≤ 1
Week 4	29	[2, 71]
Week 16	113	[72, 155]
Week 28	197	[156, 239]
Week 40	281	[240, 323]
Week 52	365	[324, 407]
Week 64	449	[408, 491]
Week 76	533	[492, 575]
Week 88	617	[576, 673]
Week 104	729	[674, 785 ^a]

Rx Day calculated relative to first dose date of risankizumab.

a. The minimum of upper bound and within 105 days of last dose of risankizumab.

The time windows specified in [Table 17](#), [Table 18](#), [Table 19](#), [Table 20](#), [Table 21](#) and [Table 22](#) will be used for the summary of study drug injections of each period.

Table 17. Visit Windows for Summary of Study Drug Injections for Part A1

Window Label	Target Day	Interval

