ASI Grouping	Categories (ASI)	Search Criteria	Terms to Display	Include in AE Overview (Y/N)
Serious infections, TB, fungal and opportunistic infections (including herpes zoster) (continued)	Fungal infections	Fungal infections CMQ (code 80000063)	PTs	N
	Herpes Zoster	Herpes zoster CMQ (code 80000175)	PTs	N
Malignancies	All possible malignancies	Narrow – Malignancies (SMQ 20000090)	PTs	N
	Malignant Tumours	Narrow – Malignant tumours (SMQ 20000194)	PTs	Y
	Non-melanoma skin cancer (NMSC)	Broad – Skin malignant tumours (SMQ 20000204) excluding terms identified by the Melanoma CMQ (code 80000119)	PTs	N
	Malignant Tumours excluding NMSC	'Malignant Tumours excluding NMSC' is identified by the 'Malignant Tumours' search excluding terms identified by the 'Non-melanoma skin cancer (NMSC)' search.	PTs	Y

Table 23. Areas of Safety Interest (Continued)

ASI Grouping	Categories (ASI)	Search Criteria	Terms to Display	Include in AE Overview (Y/N)
Hypersensitivity Reaction	Hypersensitivity	Narrow – Hypersensitivity (SMQ 20000214)	PTs	Y – serious events only
	Anaphylactic Reaction	Narrow – Anaphylactic reaction (SMQ 20000021)	PTs	N
Hepatic Events	Hepatic Events	Broad – Hepatic failure, fibrosis and cirrhosis and other liver damage-related conditions (SMQ 20000013) Broad – Hepatitis, non-infectious (SMQ 20000010) Broad – Cholestasis and jaundice of hepatic origin (SMQ 20000009) Broad – Liver related investigations, signs and symptoms (SMQ 20000008) Narrow – Liver-related coagulation and bleeding disturbances (SMQ 20000015)	PTs	N

Adverse Event per 100 Patient-Years of Exposure

Adverse events occurring during the entire study will be presented by event rate per 100 patient-years. These will be presented for any TEAEs, serious adverse events, and Areas of Special Interest.

AEs per 100 patient-years of exposure is defined as the number of AEs divided by the total exposure in 100 patient-years. Note that one event per preferred term per day per subject will be counted in the calculation of the number of AEs (i.e., a preferred term will not be counted twice on the same day for the same subject). See the calculation method below.

$$100 \times \frac{\text{Number of TEAEs}}{\text{Total Patient Years}}$$

where total patient years is defined as the sum of the study drug exposure (defined as date of last dose – date of first dose + 105 days (5 half-lives)) of all subjects normalized by 365.25, and rounded to one decimal place.

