11.3 Analysis of Laboratory Data

For the assessments of laboratory data, values observed more than 105 days after the last dose of study drug will be excluded.

Listing and descriptive statistics of laboratory values over time, changes from baseline, and extreme abnormal value on treatment will be provided. Extreme abnormal value is the value which is most significantly away from the reference range. Frequency of subjects with transitions relative to reference range and listing of subjects with significant abnormal laboratory values will be presented as well.

Analyses will be conducted in the Safety_A1 Population, the Safety_B_R Population, and the ALL_RZB Population.

For subjects who were re-randomized to placebo in Part B, laboratory values evaluated after 105 days from the last dose of risankizumab in Part A and before the first dose of retreatment will not be included in the summaries for the ALL_RZB Population.

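### The SAP's 105-day limit on safety data removes on-schedule end-of-observation visits, 112 days after the last dose, from its own Week 104 laboratory, ECG and vital-sign rows

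*SAP*

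**What the plan says.** **The limit.** SAP 11.3: "For the assessments of laboratory data, values observed more than 105 days after the last dose of study drug will be excluded". For the Part B population, the footnotes to SAP Tables 8 (vital signs) and 9 (laboratory, ECG) cap the Week 104 window "and within 105 days of last dose of study drug for safety analyses". For all risankizumab-treated patients (ALL_RZB), the footnotes to Tables 15 and 16 read "The minimum of upper bound and within 105 days of last dose of risankizumab". The SAP 6.0 definitions of the final observation use 105 days throughout. SAP 11.4 and 11.5 do not restate the rule; for ECG and vital signs it comes from Section 6.0.

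**Where 105 days comes from.** Protocol 5.3.7 defines a residual effect period of 15 weeks after the last administration and treats later adverse events as post-treatment.

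**The visit schedule.** Protocol 6.2.2 places the last dose at the end-of-treatment (EOT) visit and has all study procedures done before dosing. Protocol 6.2.3: "The follow-up period within this trial is 16 weeks after receiving the last dose of study medication". EOO closes that period. SAP 4.2 agrees: follow-up visits at 6 and 16 weeks after EOT, the second being EOO.

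**Assessments between EOT and EOO.** Tables 9 and 16 have no laboratory or ECG row between Week 88 and Week 104. Flow Charts 2 and 3 show neither test at Follow-up 1. The corresponding rows of Flow Chart 1 are not readable in the text available. Table 8 does keep a Week 94 row for vital signs.

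**The concern.** The SAP sets up Week 104 rows for laboratory, ECG and vital-sign data, then applies a rule that shuts out any patient who attends on the planned day. The rows would be filled only by patients who came early, so they would be sparse and selected by attendance.

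Laboratory and ECG data are hit hardest, because EOO appears to be the only scheduled assessment after the final injection. For a patient who completes treatment on schedule, the final value becomes the EOT sample, drawn before that injection. Hepatic injury is the protocol's one named adverse event of special interest. An abnormality first seen at an on-schedule EOO visit would be absent from the shift tables and from the Grade 3+, liver and Hy's Law listings. The data are collected, but no post-treatment display is planned for them.

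**Working it through.** **1. The two intervals.** Limit: 15 × 7 = 105 days. EOO: 16 × 7 = 112 days. Difference: 7 days.

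**2. The SAP's own window tables**, with the last dose on the Week 88 target day. Cut-off day = Week 88 target + 105.

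| SAP table | Week 88 target | Week 104 target | Gap | Cut-off day | Stated interval | Interval left |
|---|---|---|---|---|---|---|
| 8 (vital signs, Part B) | 421 | 533 | 112 | 526 | 499–568 | 499–526 (28 of 70 days) |
| 9 (laboratory/ECG, Part B) | 421 | 533 | 112 | 526 | 478–589 | 478–526 (49 of 112 days) |
| 15 (vital signs, ALL_RZB) | 617 | 729 | 112 | 722 | 674–785 | 674–722 (49 of 112 days) |
| 16 (laboratory/ECG, ALL_RZB) | 617 | 729 | 112 | 722 | 674–785 | 674–722 (49 of 112 days) |

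In all four, the target day is 7 days past the cut-off.

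**3. Other schedules.**
- Flow Chart 2 puts EOT at Day 112 and EOO at Day 224 of retreatment: 224 − 112 = 112 days. Flow Chart 3 puts EOO at EOT + 16 weeks. Both have the same problem.
- Arm 2 starts risankizumab at Week 16. In ALL_RZB its last dose falls on Day (88 − 16) × 7 + 1 = 505 and EOO on Day (104 − 16) × 7 + 1 = 617. The gap is again 112 days, so EOO is excluded. Day 617 is also the Week 88 target in Tables 15 and 16, so Arm 2 could not reach the Week 104 row even without the cap.

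**4. Share of EOO visits kept.** The documents give windows but no distribution of visit dates, so timing is an assumption. A visit is kept if its gap from the last dose is at most 105 days.
- Window of ±7 days counted from the last dose, uniform: only the visit exactly 7 days early is kept, 1/15 = 6.7%.
- Dose and EOO dates each uniform over ±7 days around targets counted from Day 1 (the rule in Protocol 6.1): of 15 × 15 = 225 pairs, 8 + 7 + … + 1 = 36 have a gap of 105 or less, 36/225 = 16%.
- Both dates within ±3 days: 0%.
- Rounded normal timing, SD 2 to 4 days: about 0.1% to 11%.

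For scale, take the 306 re-randomised patients in the sample-size calculation and suppose that all reached Week 104 without retreatment. The Part B laboratory row would then hold 306/15 ≈ 20 to 306 × 0.16 ≈ 49 of them.

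**5. Would a longer day limit do?** Share kept under the two uniform assumptions:

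| Limit | Window from last dose | Both dates drift |
|---|---|---|
| 112 days | 8/15 = 53% | 120/225 = 53% |
| 119 days | 100% | 197/225 = 88% |
| 126 days | 100% | 100% |

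A limit of 112 + 7 = 119 days can still lose in-window visits. A row defined by the visit does not.

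**The case against.** The strongest defence is that 105 days is deliberate. It is the protocol's residual effect period, it matches the SAP's treatment-emergent window, and SAP 11.3 itself refers to extreme values on treatment. That stands, and it is a good reason to keep the limit for on-treatment summaries. It does not explain a Week 104 row that the limit nearly empties, or the lack of any post-treatment laboratory or ECG display.

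Safety reporting is also not blind to late events. Laboratory results reach the investigator and sponsor in real time (Protocol 5.3.3), hepatic injury is reported on the serious-event timeline (Protocol 5.3.6.1 and 5.3.7), and SAP 11.2.2 lists all serious events. This stands: the gap is in the planned analysis, not in patient monitoring.

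A reader might infer more than the documents support:

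- **That no value after the last dose appears anywhere.** Early EOO visits are kept, and Part B vital signs have Week 94 (463 − 421 = 42 days). Patients who stop drug early may have other visits within 105 days. Patients with Grade 3+ values have the whole course of that parameter listed.
- **That the SAP departs from Protocol 7.3.4 on laboratory data.** Data "observed at screening, baseline, during the course of the trial and at the end-of-trial evaluation will be assessed", but the subject of that sentence is vital signs, physical examinations and other safety-relevant data. Laboratory data have their own paragraph, with no end-of-trial commitment.
- **That 105 days is miscalculated.** SAP 11.2.1 writes "105 days (5 half-lives" with a closing bracket, and the clearance and volume in Protocol 1.2 give ln 2 × 10.8/0.33 = 22.7 days, or 105/22.7 = 4.6 half-lives. The protocol states no half-life. This is a ratio of Phase I group means, against an implied 105/5 = 21 days, and the phrase belongs to an event-rate denominator. It shows no error.
- **That Flow Chart 3 patients keep only one on-drug laboratory value.** Their values from risankizumab treatment before relapse remain.
- **That about 500 patients lose drug-safety data.** On the protocol's assumptions, 400 × 0.8 × 2/3 ≈ 213 are re-randomised to placebo. Unless retreated, their last risankizumab dose is at Week 16.

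**Conclusion.** The SAP contradicts itself. Its 105-day limit excludes on-schedule EOO visits from the Week 104 rows of Tables 8, 9, 15 and 16, whose target days lie 112 days after the last dose. This follows from the documents' own figures.

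The share kept, about 7% to 16%, rests on uniform timing within the ±7-day windows; tighter attendance takes it towards zero. That laboratory and ECG have no other scheduled assessment after the final dose is read from SAP Tables 9 and 16 and Flow Charts 2 and 3, and for the main schedule it is an inference. For patients who complete treatment on schedule, the result is that essentially no scheduled laboratory or ECG value after the last injection is summarised.

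This should be fixed before database lock. It does not touch the efficacy conclusions or the Week 16 placebo comparison, and the safety analysis is descriptive.

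**What to change.** 1. Keep the 105-day limit for on-treatment summaries and for the final observation.
2. In Tables 8, 9, 15 and 16, define the Week 104 row by the EOO visit itself, without the 105-day cap, and label it post-treatment follow-up. Defining it by visit avoids the losses of a longer day limit and keeps Arm 2's Day 617 value out of the Week 88 row in ALL_RZB.
3. Add a matching EOO row for patients retreated under Flow Charts 2 and 3.
4. Extend the Grade 3+, liver and Hy's Law listings through EOO, flagging values more than 105 days after the last dose.
5. Keep the existing exclusion of the placebo gap from ALL_RZB.
6. State in SAP 11.4 and 11.5 which window applies to vital signs and ECG, so that the rule does not rest on table footnotes.

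The cost is SAP wording and programming; no new data are needed. The downside is an extra row and a flag, showing values slightly beyond the residual effect period, which the label makes plain.

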11.3.1 Variables and Criteria Defining Abnormality

Clinical laboratory tests conducted in the study are listed in [Table 24](#).

Table 24. Clinical Laboratory Tests

Category	Test Name
Haematology	Hematocrit (Hct) Hemoglobin (Hb) Glycosylated Hb (HbA1c) White Blood Cells/Leukocytes Platelet Count/Thrombocytes
Diff. Automatic	Neutrophils (relative and absolute count) Eosinophils (relative and absolute count) Lymphocytes (relative and absolute count)
Enzymes	AST (GOT) ALT (GPT) Alkaline Phosphatase (AP) Creatine Kinase (CK) Gamma-Glutamyl Transferase (GGT/γ-GT) Lactic Dehydrogenase (LDH) Amylase Lipase
Electrolytes	Calcium Sodium Potassium
Substrates	Glucose BUN Uric acid Creatinine eGFR (estimated by CKD-EPI formula) Bilirubin Total Albumin C-Reactive Protein (high sensitivity) Cholesterol, total Triglycerides LDL-Cholesterol (calculated) HDL-Cholesterol
Urinalysis (Stix)	Urine Protein Urine Glucose

